Communication and Coping Randomized Clinical Trial

[name], Department of Pediatric Endocrinology, VUMC

[name], Associate Professor
Department of Pediatrics
Vanderbilt University

Table of Contents:

Study Schema

- 1.0 Background**
- 2.0 Rationale and Specific Aims**
- 3.0 Animal Studies and Previous Human Studies**
- 4.0 Inclusion/Exclusion Criteria**
- 5.0 Enrollment/Randomization**
- 6.0 Study Procedures**
- 7.0 Risks of Investigational Agents/Devices (side effects)**
- 8.0 Reporting of Adverse Events or Unanticipated Problems involving Risk to Participants or Others**
- 9.0 Study Withdrawal/Discontinuation**
- 10.0 Statistical Considerations**
- 11.0 Privacy/Confidentiality Issues**
- 12.0 Follow-up and Record Retention**

Description of Amendments

Date	Affected Section(s)	Summary of Revisions Made	Rationale
3-1-19	Study Procedures	Addition of the Satisfaction Survey at the 3-Month Study visit. Removal of the Dad's Active Support Scale (DADS)	Added to evaluate acceptability of the intervention. Removed to reduce the burden for participants. Measure was only valid for heterosexual couples. Additional questions added to Demographic questionnaire to capture secondary caregiver information.
4-16-19		Change to wording in recruitment script to obtain verbal consent for screening survey	Added the wording: "You are free to skip questions you do not wish to answer; however, this may affect your eligibility for the study." to let the participant know that skipping questions would affect eligibility.
6-17-19	Inclusion/Exclusion Criteria	Addition of Parent Diabetes Distress Scale (Parent-DDS) as a measure of eligibility. Participant can either score 2 or higher on the Parent-DDS or have a score of 5-19 on the Patient Health Questionnaire 9 (PHQ-9) to be eligible.	In response to lower than expected enrollment, we expanded eligibility to include mothers who report clinically significant diabetes distress and who may benefit from intervention. We also expanded eligibility to include mothers who use Facebook 2-4 days a week rather than at least 5-6 days a week.
6-17-19	Enrollment/Randomization	Mother will be friended on Facebook during enrollment rather than sent an email.	Ensures that mother gets into Facebook group on the day of enrollment.
8-19-19	Risks	Addition of the Youth Self Report procedure to protocol. If individuals mark item 18 or 91 on the YSR (items pertaining to suicide or self-harm), KSP will follow a protocol to ensure the safety and access to resource for the individual.	Formalized protocol to further assess and provide resources to teens that may be at risk for self-harm or suicide.
4-23-20	Study Procedures Consent	Expansion the satisfaction survey at the 3-month follow-up visit. Addition of the option for mothers assigned to the education group to receive the intervention materials after final data collection. Addition to the consent that investigators from	1) Addition of questions to the satisfaction survey to capture more information about the Facebook component of the program. 2) Several participants have expressed interest in learning coping strategies included in the intervention materials.

Date	Affected Section(s)	Summary of Revisions Made	Rationale
		the University of Connecticut would have access to some participant data.	
5-26-20	Study Procedures	COVID-19 related changes to protocol, including remote enrollment and data collection and additional survey questions to assess the impact of COVID-19 on adolescents with type 1 diabetes and their mothers.	Given the COVID-19 pandemic and social distancing requirements, we have made changes to our protocol to allow for remote enrollment and data collection. We are also adding measures to assess the impact of COVID-19 on our study participants.
9-25-20	Study Procedures	The parent-child video interaction recordings for the baseline and 6-month time points will be done over ZOOM rather than in person because of the Covid-19 restrictions and social distancing. This is a temporary change because of Covid-19, therefore we will report this to the IRB as a continuing review and retract this amendment.	Covid-19 restrictions and social distancing require us to do the video interactions over ZOOM so families who feel uncomfortable with in person data collection can still participate in all parts of the study.
10-5-20	Compensation	Study personnel will confirm each gift card serial number with the order invoice to ensure the gift card record reflects the accurate monetary value.	Protocol deviation occurred due to incorrect record keeping of Amazon gift card serial numbers. Gift cards worth \$20 were incorrectly recorded by study personnel as worth \$30. Therefore, \$20 compensation was given to 4 dyads instead of the sufficient amount of \$30. This was identified by comparing the gift card serial numbers with the numbers listed on the order invoice.
10-28-20	Study Procedures + Consent	Optional qualitative interviews for study participants to assess the impact of COVID-19 on diabetes management, stress and coping.	We received supplemental funding from NIDDK to study the impact of COVID-19 on diabetes management, stress and coping. Qualitative interviews will be conducted with current participants (adolescents with type 1 diabetes and their mothers) to address the following aims: 1. To understand how the experience of COVID-19 affects the routines and health behaviors of youth with T1D and their caregivers as various levels

Date	Affected Section(s)	Summary of Revisions Made	Rationale
			of social distancing requirements are reduced. 2. To determine how the experience of COVID-19 affects mothers already experiencing diabetes distress and/or depressive symptoms and how mothers' experiences relate to their coping, social support and distress, with an emphasis on understanding what is similar to and different from their experiences with T1D prior to COVID-19.
11-3-20		The non-compliance submitted for this study on October 5th was submitted in error and should be removed.	
12-8-20	Consent	Discussed with the study team to prevent future occurrences.	The moderator posted to the Facebook study page, rather than to the private study groups. As such, mothers who were assigned to the intervention condition and control condition all received the post.
6-8-21	Recruitment	We have drafted language for distributing information about our study on Research Match and the Vanderbilt Research Notifications Distribution list to expand our recruitment efforts.	We are planning on recruiting through Research Match and the Vanderbilt Research Notifications Distribution list to reach more potential participants.
7-7-21	Recruitment	We are requesting approval to recruit using the Research Notification Distribution List and we are uploading language specifically for the Research Notification Distribution List with the contact information for our study.	We are requesting approval to recruit using the Research Notification Distribution List and we are uploading language specifically for the Research Notification Distribution List with the contact information for our study.
8-24-21	Consent	We will conduct training with the study team to clarify which protocols require a verbal consent and which protocols require a	Four participant dyads verbally consented to participate in the Covid Interview supplemental study but did not sign the consent and assent documents prior to completing the

Date	Affected Section(s)	Summary of Revisions Made	Rationale
		written consent/assent.	supplemental interviews. We are now in the process of contacting these participants to sign the consent documents.
8-25-21	Study Procedures	We are adding questions to the parental COVID-19 supplemental measure.	In order to remain up-to date on how COVID-19 is impacting our current participants, we need to add additional questions to our COVID-19 survey measure. These additions are related to COVID-19 vaccination status and the use of telehealth clinic visits. Many COVID-19 restrictions currently in place (locally and domestically) are dependent on vaccination status. We will be asking participants if any adults (18+) and children (12-17) have been vaccinated in their household. Also, we are asking if their child has seen their diabetes provider via telehealth visit since this could impact their quality of care and one of our specific study aims (glycemic control). These will only be applied to the parent surveys.
3-9-22	Consent + Compensation	We want to offer \$20 gift cards for completion of 6-month parent-child interaction videos to incentivize collection of this data point. These gift cards will be funded by the VUMC Division of Pediatric Psychology.	We were not able to collect parent-child interaction videos at baseline or the 6-month time point during the transition to a remote protocol, and we are not able to use 6-month videos that would not have a corresponding baseline video. Because of this, we have collected less 6-month videos than expected. Also, because of the switch to a remote protocol, we have several participants that will complete all other components of their 6 month follow up visit but will not schedule a time to collect the video with our team. We want to offer \$20 gift cards for completion of 6-month videos to incentivize collection of this data point.
9-1-22	Study	Change in study coordinator from	

Date	Affected Section(s)	Summary of Revisions Made	Rationale
	Coordinator	[name] to [name] (currently KSP).	

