2.0 Rationale and Specific Aims

Based on the Transactional Stress and Coping Model, which views chronic illness as a stressor to which children and mothers attempt to adapt, the ways in which mothers cope with the stress of diabetes play an important role in both maternal and adolescent adjustment to the disease. The proposed study is based on the premise that, by reducing mothers' depressive symptoms and improving the quality of parental involvement, we will improve outcomes in adolescents with T1D. Building on effective interventions to treat depression in adults, and our own pilot work in this population, the proposed study will use a rigorous approach to evaluate the efficacy of a cognitive-behavioral intervention for mothers of adolescents with type 1 diabetes to promote the use of adaptive coping strategies and positive parenting practices.

The specific aims of this project are:

1. Evaluate the efficacy of the Communication & Coping intervention as compared to an attention control condition on adolescents' diabetes outcomes (i.e., glycemic control, adherence) over 12 months. We will examine whether these effects were driven by the targeted mediators (maternal depressive symptoms, parental involvement).

Hypothesis: The adolescents of mothers who receive the intervention will demonstrate better glycemic control and better adherence to treatment than those in the attention control condition.

2. Evaluate the efficacy of the Communication & Coping intervention as compared to an attention control condition on adolescents' psychosocial outcomes (i.e., adolescent depressive symptoms and quality of life) over 12 months.

Hypothesis: The adolescents of mothers who receive the intervention will report better quality of life and fewer depressive symptoms than those in the attention control condition.

Exploratory Aim: Examine the differential impact of intervention effects across demographic factors (i.e., marital status, income, adolescent age, and sex).

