At baseline and 6 months data collection, adolescent-mother dyads will participate in a 15-minute videotaped conversation about diabetes-related stress. To choose the topic for the video interaction, we will use the mother's highest-rated stressor on the Response to Stress Questionnaire (Connor-Smith, Compas, Wadsworth, Thomsen, & Saltzman, 2000), completed as part of the survey data collection, which lists diabetes-specific stressors. Mothers will rate the frequency of each stressor (e.g., worrying about "bad" numbers, remembering diabetes supplies) on a 4-point Likert scale ranging from 0 (never) to 3 (almost every day). Each dyad will be given a cue card with questions regarding the highest-rated stressor (e.g., What happened the last time we [had to] you remember diabetes supplies], what kind of emotions do we have when we [have to remember diabetes supplies]? How can we reduce this stress?) to guide their discussion during the videotaped interaction. This protocol has been used successfully in other studies conducted by [name], and she has trained several cohorts of raters on the Iowa Family Interaction Rating Scales to be reliable coders.

The interaction will be recorded using study iPads. Video files will be transferred from the passcoded iPad to an encrypted study computer, and then uploaded to Enterprise Storage, the secure, shared drive. Video files will only be viewed by KSP.

Mothers in the study will have 7 individual phone calls with a trained member of our research staff to discuss the information in the binders. Calls will last approximately 10-30 minutes. Mothers assigned to the Communication & Coping group will discuss content related to coping with diabetes-related stress and positive parenting strategies, following the study manual mailed to participants after randomization. The content of this manual was reviewed by a coder trained in health literacy at Vanderbilt's Effective Health Communication Core. Each session was given a Suitability Assessment of Materials (SAM) score to objectively assess the materials for clear communication and health information design (content, literacy demand, graphics, layout and typography, learning stimulation, and cultural appropriateness). Scores of 70% to 100% are considered superior material suitable for low health literacy individuals (Doak, Doak, & Root, 1996). On the SAM scale, our sessions were rated 78% to 86%, with a reading

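### Requiring a baseline value before a 6-month video score can be used gives up usable information and is not needed for validity

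*Combined protocol and SAP*

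**What the plan says.** Section 6.0 schedules the recording twice and attaches no pairing condition: "At baseline and 6 months data collection, adolescent-mother dyads will participate in a 15-minute videotaped conversation about diabetes-related stress". It points to scoring by trained raters, saying of the investigator concerned that "she has trained several cohorts of raters on the Iowa Family Interaction Rating Scales to be reliable coders".

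The 3-9-22 entry in the Description of Amendments explains why gift cards were added for 6-month videos. Recordings could not be made while the study moved to remote procedures, and "we are not able to use 6-month videos that would not have a corresponding baseline video". The entry continues: "Because of this, we have collected less 6-month videos than expected". It gives a second, separate cause of loss, namely families who "will complete all other components of their 6 month follow up visit but will not schedule a time to collect the video with our team".

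Section 10.0 plans linear mixed models for the continuous outcomes. Baseline is one of the time points, and treatment and treatment-by-time are the main terms. A subject enters only with a baseline value and a 6- or 12-month value. The video scores are not mentioned there by name.

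Section 5.0 places random assignment after the baseline data are complete, with equal allocation.

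**The concern.** In a randomised trial the arms are comparable at 6 months whether or not a baseline score exists. A baseline score improves precision; it is not a condition for using the later score. Making it one loses every dyad whose baseline recording was missed, and those dyads come largely from one period, the move to remote enrolment.

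At stake is the only measure of how mother and adolescent interact that does not rest on a questionnaire. Under the rule, its result would have wider intervals than necessary and would describe mainly families enrolled outside that period. The study is also paying to raise the number of 6-month videos while setting aside some that could be used.

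**Working it through.** **Inputs from the documents.** The only within-subject correlations given are 0.60 for A1C (SD 1.16%) and 0.82 for the SCI (Section 10.0, power and sample size). The planned analysed sample is 130 of 154 enrolled. No SD, correlation, sample size or count of missing recordings is given for the video measure.

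**Step 1. Reproduce the plan's own figure.** This confirms how the plan uses its correlations. With m measurements and compound symmetry, the variance of a subject mean is SD² × (1 + (m − 1)ρ)/m. The total N for a 0.5% difference, 80% power and two-sided 0.05 is 4 × (1.96 + 0.84)² × variance / 0.5².

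- m = 4: variance 1.3456 × 0.70 = 0.942. N = 118.3, or 120 in equal arms, and 122 with the t distribution. Stated: 122.
- m = 2: variance 1.3456 × 0.80 = 1.076. N = 135.2, or 136 in equal arms, and 138 with the t distribution. Stated: 138.

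Both figures reproduce.

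**Step 2. Information in an unpaired 6-month score.** With unit variance and a common baseline mean (or ANCOVA), a complete pair contributes 1/(1 − ρ²) to the 6-month arm difference and a 6-month-only dyad contributes 1. The ratio is 1 − ρ².

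| ρ | Share of a complete pair |
|---|---|
| 0.4 (assumed) | 84% |
| 0.60 (A1C value) | 64% |
| 0.82 (SCI value) | 33% |

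The share exceeds one half only if ρ is below √0.5 = 0.71.

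**Step 3. Effect on the standard error.** The reduction from including n unpaired dyads alongside 80 pairs is 1 − √(I/(I + n)), with I = 80/(1 − ρ²). I is 95.2, 125.0 and 244.2 at the three correlations. The 80 and all values of n are assumptions.

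| n unpaired | ρ = 0.4 | ρ = 0.6 | ρ = 0.82 |
|---|---|---|---|
| 10 | 4.9% | 3.8% | 2.0% |
| 30 | 12.8% | 10.2% | 5.6% |
| 50 | 19.0% | 15.5% | 8.9% |

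**Step 4. Dependence on the model.** Take 130 dyads with a 6-month score, 20% of them (26) without a baseline, and ρ = 0.60. The difference detectable with 80% power is 2.80 × √(4/information).

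- Common baseline mean, unpaired dropped: information 104/0.64 = 162.5, detectable 0.44 SD.
- Common baseline mean, unpaired kept: 162.5 + 26 = 188.5, detectable 0.41 SD.
- Baseline arm difference left free, effect read from treatment-by-time: 0.49 SD dropping them and 0.48 SD keeping them.

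In the free-baseline model, keeping unpaired dyads recovers only a small part of the information lost through missing baselines: 24–33% at ρ = 0.3, 13–18% at 0.60 and 6–8% at 0.82, with 10–40% of dyads assumed to lack a baseline. The gain therefore needs the common baseline mean as well as the wider inclusion rule.

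**The case against.** Several points on the other side have force.

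*The amendment entry is a rationale, not an operative rule.* True. Section 6.0 already schedules the 6-month video without a pairing condition. But the live inclusion rule in Section 10.0 also demands a baseline value, and nothing in Section 6.0 or 10.0 exempts the videos. The entry shows how the study team understands the matter.

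*A reader might infer that a stock of recordings is being thrown away.* The documents do not show this. The entry speaks of videos that would lack a baseline and of fewer being collected, so many were probably never made, and families who did not schedule are a separate loss that the pairing rule did not cause. By the log's dates, remote enrolment was added on 5-26-20 and Zoom recording on 9-25-20. A dyad enrolled between them reached 6 months by about March 2021, a year before the 3-9-22 entry. Zoom was available for many of those visits, so the pairing rule may be why some were not recorded, but that is an inference.

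*A reader might infer that most of the information is lost.* That requires ρ below about 0.71 and a common baseline mean. It fails at the SCI correlation, and it fails at every correlation tried (0.3 to 0.82) if the baseline arm difference is left free, which is a plain reading of the Section 10.0 model.

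*A reader might infer that the trial has no other objective outcome, or that a stated aim rests on the video.* Neither holds. HbA1c is a laboratory value. Aim 1 names "adolescents' diabetes outcomes (i.e., glycemic control, adherence) over 12 months" and Aim 2 "adolescents' psychosocial outcomes (i.e., adolescent depressive symptoms and quality of life) over 12 months". The video is in neither, and it cannot serve as the 3-month mediator because it is not recorded then.

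*The larger illustrative counts are strained.* Fair: 80 + 50 uses all 130 planned analysable dyads, and 30 to 50 is about 19% to 32% of 154. The row with 10 is included for this reason.

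**Conclusion.** The concern stands as one of efficiency and coverage. The baseline condition is unnecessary for a valid 6-month comparison and gives up between about one third (ρ = 0.82) and five sixths (ρ = 0.4) of a complete pair's information for each dyad that has, or could have had, a 6-month video alone. Over the assumed counts, the standard error of the 6-month arm difference would fall by between 2% and 19%. The true figure cannot be fixed from the documents.

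This rests on three assumptions: a common baseline mean, which randomisation justifies; the baseline video being among the data completed before assignment, as Section 5.0 implies; and correlations borrowed from other measures. On the second assumption, a missing baseline video precedes allocation and so does not bias the comparison between arms. Failure to schedule the 6-month video occurs after allocation and is a different problem, which this change does not address.

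**What to change.** - In Section 10.0, lift the baseline-value condition for the video scores, and state an analysis for them, since none is given. Enter the baseline and 6-month scores as responses in a mixed model with one baseline mean shared by both arms and a treatment effect at 6 months, so that 6-month-only dyads count.
- Report the analysis restricted to complete pairs as a sensitivity analysis, with the number of paired and unpaired dyads in each arm.
- Code any unpaired 6-month recordings already held, and collect the 6-month video from every dyad that has not yet passed that visit, as Section 6.0 already schedules.

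The cost is a sentence or two of analysis wording, rater time for a few extra 15-minute recordings, and the $20 card already planned for 6-month videos. The benefit is limited to recordings that exist or can still be made.

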1.0 Background

Mothers of adolescents with type 1 diabetes (T1D) experience high levels of depressive symptoms, which impair their ability to monitor and manage diabetes treatment effectively. The regimen recommended for type 1 diabetes is complex and demanding, and caregivers - especially mothers - experience stress related to the burden of treatment management. This stress is associated with increased risk for psychosocial problems in caregivers, with rates of clinically significant symptoms of depression evident in up to 61% of parents. Further, maternal depressive symptoms are one of the strongest predictors of negative outcomes in adolescents, including deteriorating glycemic control, problems with adherence, poorer quality of life, and greater risk for depression. Given that adolescents are a high-risk population for suboptimal glycemic control - with only 17% meeting treatment goals - there is a critical need for novel interventions to improve outcomes in adolescents with T1D. Yet, previous behavioral interventions for youth with diabetes have had only modest effects on glycemic control, many were time- and resource-intensive, and none have directly targeted maternal depressive symptoms.

2.0 Rationale and Specific Aims

Based on the Transactional Stress and Coping Model, which views chronic illness as a stressor to which children and mothers attempt to adapt, the ways in which mothers cope with the stress of diabetes play an important role in both maternal and adolescent adjustment to the disease. The proposed study is based on the premise that, by reducing mothers' depressive symptoms and improving the quality of parental involvement, we will improve outcomes in adolescents with T1D. Building on effective interventions to treat depression in adults, and our own pilot work in this population, the proposed study will use a rigorous approach to evaluate the efficacy of a cognitive-behavioral intervention for mothers of adolescents with type 1 diabetes to promote the use of adaptive coping strategies and positive parenting practices.

The specific aims of this project are:

1. Evaluate the efficacy of the Communication & Coping intervention as compared to an attention control condition on adolescents' diabetes outcomes (i.e., glycemic control, adherence) over 12 months. We will examine whether these effects were driven by the targeted mediators (maternal depressive symptoms, parental involvement).

Hypothesis: The adolescents of mothers who receive the intervention will demonstrate better glycemic control and better adherence to treatment than those in the attention control condition.

2. Evaluate the efficacy of the Communication & Coping intervention as compared to an attention control condition on adolescents' psychosocial outcomes (i.e., adolescent depressive symptoms and quality of life) over 12 months.

Hypothesis: The adolescents of mothers who receive the intervention will report better quality of life and fewer depressive symptoms than those in the attention control condition.

Exploratory Aim: Examine the differential impact of intervention effects across demographic factors (i.e., marital status, income, adolescent age, and sex).

